### **Risks Pertaining to Loss of Confidentiality and Privacy.**

Identifying information will be collected only for the purpose of contacting participants for their longitudinal follow-up assessments. All study computers are password protected and housed in the PI's lab space at either Muenzinger Hall or the CINC, which are both kept locked unless researchers or students are currently using the space. Further, there is no identifying information contained on the laptops. All identifying information (e.g., consent forms, contact information) is kept separate and secure from the data files and never on the same laptop and this information will be destroyed immediately after the last follow-up.

Participants will be informed that we are required to report information like child abuse or neglect, crimes that they tell us they or others plan to commit, or harm planned against yourself or others.

### **XVII. POTENTIAL BENEFITS**

---

These studies are expected to add to the knowledge base of information on the development and treatment of alcohol use disorder. Given only a slight risk to participants and the greater possibility of long-term benefits to the knowledge base and to treatment interventions for alcoholics, the risks/benefits ratio seems reasonable. As a part of this study, all participants will have the opportunity to examine their own alcohol use behavior in the context of completing measurement instruments, and will have the opportunity to work with a trained therapist over the course of the trial. Participants will also receive the added benefit of a treatment (either MBRP or RP) that has demonstrated efficacy in the treatment of AUD. The risks associated with participating have been minimized via the procedures described above. Finally, a demonstration that MBRP is superior to RP and the identification of the mechanisms of action has great potential to benefit others.

### **XVIII. PROVISIONS TO MONITOR THE DATA FOR THE SAFETY OF PARTICIPANTS**

---

We have taken a number of measures to ensure the confidentiality of the data and the safety of the participants. All data from the proposed study will be identified by a numerical ID code only. The information linking the numerical ID code to identifying information will be maintained separate and secure from the data themselves. At the conclusion of the final follow-up data collection, the list linking the ID code to identifying information will be destroyed.

It will be the responsibility of the PI to obtain and maintain approval of all procedures from the Internal Review Board (IRB). Study staff will report to the PI on a weekly basis regarding the procedures being employed in the protocol to assure that all IRB-approved procedures are being followed. Any adverse events will be reported to the PI immediately. The PI will immediately call the IRB to inform the secretary and the committee of the adverse event. The PI will submit a detailed description using the HRP-214 New Information Form in eRA to report all adverse events consistent instructions of CU Boulder IRB's List of Standard Operating Procedures document: ([http://www.colorado.edu/vcr/sites/default/files/IRB-Policies-and-Procedures\\_05012013.pdf](http://www.colorado.edu/vcr/sites/default/files/IRB-Policies-and-Procedures_05012013.pdf)). Consistent with IRB policy, the reporting will occur immediately (within 24 hours) upon learning of a study-related death, study personnel will notify the IRB via e-mail by providing a brief summary of the event. Then, within 1 week (five business days), the PI or designee will submit a Reportable Event in eRA. (2) For any other problem or event requiring reporting to the IRB, the PI or designee will submit to the IRB a Reportable Event or Deviation in eRA as soon as possible, but no later than 10 working days from notification of event.

In addition, the proposed study will form and utilize a Data Safety and Monitoring Board (DSMB) at the University of Colorado. This DSMB will consist of individuals with broad range of clinical and research experience. The DSMB members will include a psychiatrist (e.g., [name]) a clinical psychologist working in a non-profit addiction center (e.g., [name]), and individual with extensive experience in research ethics who is also a member of the IRB (e.g., [name]). The DSMB is intended to ensure the safety of our research participants, the validity of the data, and the appropriate termination of the proposed study based on any emergent significant benefits or risks. For these reviews the DSMB will review any adverse events and any safety differences that are emerging between the randomized arms at intervals of every three months. To facilitate this review, the PI will provide the DSMB with the data related to safety and efficacy. If the DSMB determines that there are significant emergent risks, the DSMB will make a recommendation to the PI and IRB that the study be closed for accrual of participants until a more detailed review can be conducted in conjunction with the PI and IRB. Ultimately, the study may be terminated depending on the outcome of this review.

The MRI technologists are not trained to identify potentially significant clinical anomalies in the brain images. Should the MRI technologist notice something he or she believes to be a potential anomaly in a brain image, he or she will follow the procedure noted in section XVII to ensure appropriate radiological review. The participant will be contacted if the radiologist recommends a scan to determine the clinical significance of any anomaly.

Lastly, a potential risk that the study team will be prepared to manage is participant endorsement of thoughts of suicide on the Beck Depression Invention (BDI-II). The BDI-II is used to measure depression symptomatology. Item number 9 from the BDI-II inquires about “suicidal thoughts or wishes” that participants may or may not be experiencing. In order to ensure the safety of our participants, a staff member will check the participant’s response to item number 9 of the BDI-II before the participants leaves the building. If a participant has either responded “I would like to kill myself” or “I would kill myself if I had the chance,” the research team member will immediately notify [name] (a licensed clinical psychologist). [name] or a master’s-level clinician will immediately assess the participant for imminent suicide risk and provide him/her with a list of psychological services referral contacts. After the participant has been assessed for risk, the study coordinator will use the CU CHANGE lab’s previously IRB approved ‘Suicide Ideation Protocol’ to connect the participant with an appropriate referral resource (i.e., 911 if in imminent danger, Boulder County Mental Health Center (BCMHC) if the participant is a community member, or Wardenburg Health Center and/or BCMHC if the participant is a CU Boulder student, staff, or faculty member). [name] himself or a research team member will follow up with [name] to ensure that all of the necessary measures had been taken to protect the safety of the participant and determine whether or not it is safe for the participant to continue their involvement in the study. If it is determined that the participant is at imminent risk and should not continue participating in the study, [name] will contact the participant and explain that for their safety, the research team does not feel that it is safe for him/her to continue participating in the study and will also answer any questions the participant may have about this decision.

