
Participants will be instructed to arrive at the CINC 10 minutes prior to their scheduled appointment and meet in Room 129. Participants will fill out a quick check-in survey on an iPad before their appointment begins in order to inform therapists of the extent to which they completed their home practice the week before. The check-in survey will also allow participants to record any questions they have for their therapist before the appointment begins. The room will have two chairs with a coffee table in between the chairs, along with meditation cushions. Water will be available in the room. At each session, the therapist will engage and guide the participant in a discussion and exercise. The session will last one hour.

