## **Goal-setting Session**

Subjects will have a 1-hour individual session with a trained therapist before starting the 8-week long program, resulting in a total of 9 individual therapy sessions. The purpose of this being a chance for the participant to discuss with their therapist their goals for the next 8 weeks in terms of drinking reduction goals or abstinence goals. Subjects will take a BAC test before the session starts.

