## **MBRP (or RP) Weekly Sessions**

Subjects will meet with a trained therapist for 1-hour individual therapy sessions once a week for 8 weeks at the CINC in a private consultation room.

Subjects will be breathalyzed and complete their check-in survey before every session starts. If subjects are dropped due to accumulated "missed" sessions due to failure to follow the abstinence instructions, they will not be compensated for previous attended therapy sessions. They will be informed of this contingency during the phone screen, consent visit and is stated the consent form.

Subjects will be compensated \$15 for each therapy session they complete (payment for each completed session is given to participants at week 8).

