### **Check-in Session (33 weeks)**

Those subjects who participated in the MRI scan will return for a visit with a therapist one week after their second follow-up session. Before this session starts, participants will take a BAC test. During this session, the therapist will assess whether there were any adverse events, including lapses that may have resulted from the alcohol cues administered during the MR scan. Any adverse events will be addressed in the session and reported to the PI. At the end of their last session (33 weeks), participation in the study is complete.

Name of instrument/tool/procedure	Purpose (i.e. what data is being collected?)	Time to Complete
Questionnaire Measures Collected at Baseline Only		10 minutes
Demographics	

• A demographics questionnaire will be used to collect information on age, sex, marital status, SES, occupation, income, education, and race.

	
The Stages of Change Readiness and Treatment Eagerness Scale (SOCRATES)	

• SOCRATES (Miller & Tonigan, 1996) is an experimental instrument designed to assess readiness for change in alcohol abusers. The instrument yields three factorially-derived scale scores: Recognition (Re), Ambivalence (Am), and Taking Steps (Ts). It will be used to measure individual differences in motivation at baseline.

	

---

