**FOLLOW-UP SESSIONS I & II:** At the end of this week 8 session, they will schedule their final two follow-up appointments with the research assistant. These will be scheduled at 20 weeks (3 months post-treatment) and 32 weeks (6 months post-treatment). At these two appointments, participants will fill out questionnaires via a link, and will be compensated with a \$50 Amazon gift card for completing the questionnaires at each of these two follow-up appointments. After this 32-week appointment, participation in this study will be complete.

Visit/Session	Procedures/Tools	Location	Time to Complete
Baseline Session	Informed consent; Study orientation; Questionnaires.	Remote/Zoom	1 hours and 30 minutes
Goal-setting Session	An introduction and goal-setting session with your therapist.	Remote/Zoom	1 hour
MBRP or RP, Individual Therapy Sessions (weeks 1-3 and 5-7)	Mindfulness Based Relapse Prevention or Relapse Prevention therapy session with a trained therapist.	Remote/Zoom	1 hour sessions (6 hours total)

Visit/Session	Procedures/Tools	Location	Time to Complete
Intermediate Session (at 4 weeks)	MBRP or RP therapy session; Questionnaires.	Remote/Zoom	2 hours
End of Treatment Session (at 8 weeks)	MBRP or RP therapy session; Questionnaires.	Remote/Zoom	2 hours
Follow-up Session I (at 20 weeks)	Questionnaires	Remote/Zoom	1 hour
Follow-up Session II (at 32 weeks)	Questionnaires	Remote/Zoom	1 hour
TOTAL TIME			Approximately 15 hours

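### The DSMB is asked to compare safety between arms, but general adverse events during treatment are not systematically elicited or tabulated

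*Combined protocol and SAP*

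**What the plan says.** Section XVIII gives the DSMB its task: "the DSMB will review any adverse events and any safety differences that are emerging between the randomized arms at intervals of every three months". For this, "the PI will provide the DSMB with the data related to safety and efficacy"; the contents of that package are not listed. The same section says what follows once an event is known ("Any adverse events will be reported to the PI immediately", then the IRB), but not how events are to be found.

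In section XI, treatment consists of a goal-setting session plus eight weekly sessions, "resulting in a total of 9 individual therapy sessions". At the weekly sessions, "Subjects will be breathalyzed and complete their check-in survey before every session starts". Section IV says the check-in survey is there to "inform therapists of the extent to which they completed their home practice the week before" and to let participants note questions for the therapist.

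The one explicit adverse event question is in the check-in session at week 33, for scanned participants, where "the therapist will assess whether there were any adverse events, including lapses that may have resulted from the alcohol cues". Section XVI, under Exposure to Alcohol, says instead that therapists will see every patient for the extra week. In the remote procedures of section XI there is no such visit: "After this 32-week appointment, participation in this study will be complete".

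**The concern.** A board asked to look for safety differences between arms needs events collected in the same way in both arms, with a known number of people asked. The visit schedule provides neither for general adverse events during the eight weeks of treatment. A new medical or psychiatric problem, a hospital or emergency visit, or withdrawal symptoms would come to light through conversation or chance. The therapists who hold most of these conversations necessarily know which treatment they are giving.

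If events are under-recorded equally in both arms, a real difference becomes harder to see. If they are recorded unequally, a difference can appear where there is none. The final report would have the same weakness, because the Data Analysis Plan contains no comparison of adverse events by arm.

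**Working it through.** **Step 1: contacts during treatment.** 1 goal-setting session + 6 sessions (weeks 1–3 and 5–7) + week 4 + week 8 = 9, which matches the stated total.

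**Step 2: what each contact asks, from the section XI procedures and visit tables.**

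| Contact | General adverse event question, in person | Remote |
|---|---|---|
| Goal-setting | none listed | none listed |
| Weeks 1–3, 5–7 | none listed | none listed |
| Weeks 4 and 8 | none listed | none listed |
| Week 20 | none listed | none listed |
| Week 32 | none listed; craving or anxiety check after the scan | none listed |
| Week 33 | yes, scanned participants | no visit |

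This gives 0 of 9 treatment contacts in either mode. Week 33 falls 33 − 8 = 25 weeks after treatment ends. If the section XI account of week 33 is followed, an unscanned or remote participant is never asked a general adverse event question.

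**Step 3: the prompted checks that exist.**
- *BDI-II item 9* (section XVIII). Staff check it before the participant leaves the building; the remote procedures state no counterpart. The instrument is listed among measures given at baseline and weeks 4, 8, 20 and 32, but its own description gives only baseline and last follow-up. On the second reading it is not given during treatment.
- *Critical liver values* (section XVI). The laboratory alerts the study. Remote mode collects no blood.
- *Post-scan check* (section XI, week 32; section XVI). It covers reactions to the alcohol cues.

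The documents do not say that any of these is recorded as an adverse event.

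**Step 4: illustration of what capture does.** The event rates and capture rates are assumptions; the documents give neither. Inputs: 113 per arm (Specific Aim 1), Fisher's exact test, two-sided .05. Recorded rate = true rate × proportion captured.

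| True rates | Captured | Recorded rates | Probability of p ≤ .05 |
|---|---|---|---|
| 5% v 15% | all | 5% v 15% | .64 |
| 5% v 15% | half | 2.5% v 7.5% | .30 |
| 5% v 15% | a quarter | 1.25% v 3.75% | .09 |
| 20% v 20% | all | 20% v 20% | .035 |
| 20% v 20% | 60% v 48% | 12% v 9.6% | .06 |
| 20% v 20% | 60% v 30% | 12% v 6% | .27 |

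The first three rows concern missing a real difference, the last three a false one. The false signal is large only if capture differs between arms by about two to one.

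These figures are for full enrolment. With 5% v 15% and perfect capture, power is .07 at 25 per arm (about one year at the planned 50 enrolments per year) and .24 at 50 per arm.

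**The case against.** Much information relevant to safety is collected on a schedule that is the same in both arms: drinking by TLFB, anxiety, pain interference, craving, perceived stress, sleep and use of psychological services, besides the three checks above. The board also receives efficacy data. This stands, and it limits the point to general adverse events. A reader might infer that the whole safety comparison rests on unprompted reports, or that week 33 is the only prompted safety contact. The documents support neither.

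A reader might also infer that events reach the PI only through a therapist. The documents describe other routes: research assistants stay with remote participants during treatment-period questionnaires, the coordinator contacts patients between follow-up visits, and supervisors meet weekly and review session recordings. None of these is a standard adverse event question.

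Three further inferences fail. The three-month interval does not mean the board hears nothing sooner; section XVIII sets a review interval and does not bar earlier notice. The background remark about fewer side effects compares psychosocial treatment with medications, which this trial does not test. And the documents give no basis for saying that unprompted reporting misses most events, or that it does differ between these two therapies.

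Finally, no significance test of adverse events is planned, and early reviews would have little power even with complete capture. This is correct. The case for a checklist is that the counts become comparable and have a denominator, not that a quarterly test becomes powerful. The protocol's description of the risk as slight bears on urgency, but it does not remove a task assigned to the board.

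**Conclusion.** The point holds in limited form. Apart from BDI-II item 9, critical liver values and the post-scan cue check, no visit elicits adverse events systematically, and the one explicit question comes 25 weeks after treatment to a subset of participants. The between-arm comparison of general adverse events during treatment therefore depends largely on volunteered or incidentally noticed events, and the analysis plan does not tabulate them.

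That conclusion rests on reading the procedures and needs no assumed rate. The size of the harm is not known: the fall in power from .64 to .30 or .09, and the false-signal range of .06 to .27, apply only under the assumed event and capture rates. The trial can run as written, but this DSMB task cannot be done reliably.

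**What to change.** 1. Add one identical short adverse event checklist to the existing questionnaires at weeks 4, 8, 20 and 32, in person and remote, for every randomised participant. It would ask, since the last contact, about any new or worse medical or psychiatric problem, emergency or hospital visit, and withdrawal symptoms.
2. Give the DSMB events over number of people asked, by arm, and add the same table to the analysis plan and final report.
3. State how checklist items map to the IRB reporting route in section XVIII. As written, that section has the PI call the IRB immediately and submit a form for all adverse events, so without a mapping every minor item would follow that path.
4. Reconcile sections XI and XVI on who attends week 33, and the two statements of BDI-II timing. State how the item 9 check is done remotely.

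Copying IRB reports to the DSMB as they are sent is optional.

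The cost is one amendment, about two minutes per visit in surveys already given, and more minor events to record and route.

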## **XIX. PROVISIONS TO PROTECT THE PRIVACY INTERESTS OF PARTICIPANTS**

Fully informed consent will be sought to ensure that participants are aware of any possible risks. Subjects will be aware of all study procedures, measures, and data being collected throughout the

study. Data and observations will not be collected or obtained without their knowledge or consent. Participation in the research is completely voluntary, as is answering each particular question in all of the measures and providing each physiological measure.

## **XX. MEDICAL CARE AND COMPENSATION FOR INJURY**

---

Participants will be informed to contact [name] immediately by [contact]) should they feel that they have been harmed while participating in this study. They will be told that the cost for any treatment will be billed to them or their medical or hospital insurance. Information regarding compensation for injury is included in the informed consent document.

## **XXI. COST TO PARTICIPANTS**

---

There are no costs to the participant for participation in this study aside from those accrued from transportation to and from study appointments. Participants will be compensated throughout the study, with a total of \$280 if they complete all sessions. For those subjects who are eligible and selected to participate in the MRI scan portion of the study, they will be compensated an addition \$60 (\$30 per scan) with a total of \$340 if they complete all sessions. At each session they will be compensated a given amount (described in IX.) that should cover all travel costs and parking is free at the CINC.

## **XXII. DRUG ADMINISTRATION**

---

Not Applicable.

## **XXIII. INVESTIGATIONAL DEVICES**

---

Not applicable.

## **XXIV. MULTI-SITE STUDIES**

---

Not applicable.

## **XXV. SHARING OF RESULTS WITH PARTICIPANTS**

---

There are no plans to share results of the study with individual participants.

